2.1.4.2 Deaths

The deaths observation periods are per the observation periods defined above

- Death on-study: deaths occurring during the on-study observation period
- Death on-treatment: deaths occurring during the treatment-emergent adverse event period
- Death poststudy: deaths occurring after the end of the study

2.1.4.3 Laboratory safety variables

Clinical laboratory data consists of blood analysis, including hematology, clinical chemistry, and urinalysis. Clinical laboratory values after conversion will be analyzed into standard international units and international units will be used in all listings and tables.

Blood samples for clinical laboratories will be taken at Visit 1(Week -4±1), Visit 2 (Week 0), Visit 8 (Week 12), Visit 14 (Week 24), Visit 20 (Week 36), Visit 28 (Week 52), Visit 31 (Week 64) and early termination unless otherwise specified. The laboratory parameters will be classified as follows:

- Hematology
 - **Red blood cells and platelets and coagulation:** hemoglobin, hematocrit, red blood cell count, platelet count
 - **White blood cells:** white blood cell count, neutrophils, lymphocytes, monocytes, basophils, eosinophils
- Clinical chemistry
 - **Metabolism:** glucose, total cholesterol, total protein, creatine phosphokinase
 - **Electrolytes:** sodium, potassium, chloride, bicarbonate
 - **Renal function:** creatinine, blood urea nitrogen, uric acid

- **Liver function:** alanine aminotransferase, aspartate aminotransferase, alkaline phosphatase, lactate dehydrogenase, total bilirubin (in case of values above the normal range, differentiation in conjugated and non-conjugated bilirubin), albumin
- **Hepatitis screen:** Hepatitis virus tests will be performed at Screening Visit 1, including hepatitis B surface antigen (HBs Ag), hepatitis B Surface antibody (HBs Ab), hepatitis B core antibody (HBc Ab), hepatitis C virus antibodies (HCV Ab). In case of results showing HBs Ag (negative), HBs Ab (negative) and HBc Ab (positive), an HBV DNA testing may be performed prior to randomization to rule out a false positivity if the investigator believes the patient is a false positive, or to clarify the serological status if the investigator finds it unclear to interpret in absence of known HBV infection. In case of results showing HCV Ab (positive), an HCV RNA testing may be performed to rule out a false positivity, if the investigator believes the patient is a false positive
- **HIV screen:** anti-HIV-1 and HIV-2 antibodies will be tested at Visit 1
- **Anti-nuclear antibody (ANA)** will be tested at Visit 1
- Serum immunoglobulins: quantitative immunoassays for total IgG, IgG subclasses 1-4, IgM, and IgA will be tested at Visit 2, Visit 14 (Week 24), and Visit 28 (Week 52)

Urine samples will be collected as follows:

- **Urinalysis** (limited to Visit 1(Week -4±1), Visit 8 (Week 12), Visit 14 (Week 24), Visit 20 (Week 36), Visit 28 (Week 52), and Visit 31 (Week 64)): Urine dipstick analysis specific gravity, pH, glucose, ketones, blood, protein, nitrate, leukocyte esterase, urobilinogen and bilirubin (by dipstick). If any parameter on the dipstick is abnormal, a urine sample should be sent to the central laboratory for testing. If positive for proteins, microscopic analysis is performed by central laboratory
- **Pregnancy test:** A urine pregnancy test will be performed at Screening (Visit 1) in female patients of childbearing potential who have commenced menstruating, and a urine dipstick pregnancy test will be performed at Visit 2 prior to randomization, Visit 4 (Week 4), Visit 6 (Week 8), Visit 8 (Week 12), Visit 10 (Week 16), Visit 12 (Week 20), Visit 14 (Week 24), Visit 16 (Week 28), Visit 18 (Week 32), Visit 20 (Week 36), Visit 22 (Week 40), Visit 24 (Week 44), Visit 26 (Week 48), Visit 28 (Week 52), and Visit 31 (Week 64). Those female patients who commence initial menstruation during the study will be similarly monitored with urine dipstick pregnancy tests and contraception consulting for the duration of the study

Technical formulas are described in [Section 2.5.1](#).

2.1.4.4 Vital signs variables

Vital signs blood pressure (mmHg), heart rate (beats per minute), respiratory rate (breaths per minute), body temperature (degrees Celsius), and will include height (cm) and body weight (kg), measured at the Screening and Randomization Visits (Visits 1 and 2) and every subsequent visit. Height will be measured with a proper stadiometer at every visit. Stadiometer measurements will

be made without patient wearing shoes. Vital signs will be measured at clinic visits, in sitting position, using the same arm at each visit, and prior to administration of investigational product.

2.1.4.5 Electrocardiogram variables

One recording of a standard 12-lead electrocardiogram (ECG) will be performed at Screening, Visit 28 (Week 52/EOT), and Visit 31 (Week 64/EOS). ECGs were recorded automatically by the device at the Investigator site.

2.1.4.6 Physical Examination

Physical examinations will be performed at Screening, Visit 14 (Week 24), Visit 28 (Week 52/EOT), and Visit 31 (Week 64/EOS) and will include an assessment of general appearance, skin, eyes, ear/nose/throat, heart, chest, abdomen, reflexes, lymph nodes, spine, and extremities, including menstruation status. All deviations from normal will be recorded, including those attributable to the patient's disease.

2.1.5 Pharmacokinetic variables

Predose blood samples will be collected for determination of functional dupilumab concentration in serum on Visit 2 (Week 0), Visit 5 (Week 6), Visit 8(Week 12), Visit 14 (Week 24), Visit 28 (Week 52) and Visit 31 (Week 64).

2.1.6 Anti-drug antibody (ADA) variables

Anti-dupilumab antibody (ADA) (including neutralizing antibodies) status (negative or titer value, if positive in the ADA assay) at Visit 2 (Day 1), Visit 8(Week 12), Visit 14 (Week 24), Visit 28 (Week 52) and Visit 31 (Week 64) will be provided. Patients who discontinue early from treatment or patients who choose not to participate in the LTS study visit may be asked to return to the clinic to have additional ADA samples collected for analysis based on the overall clinical presentation at that time.

ADA incidence will be classified as the following:

Pre-existing immunoreactivity is defined as:

An ADA positive response in the assay at baseline with all post treatment ADA results negative, OR an ADA positive response at baseline with all post treatment ADA responses less than 4-fold over baseline titer levels.

Treatment-emergent response is defined as:

A positive response in the ADA assay post first dose, when baseline results are negative or missing.

Treatment-emergent ADA responses are further classified as Persistent, Indeterminate or Transient

- a) Persistent Response - defined as a treatment-emergent ADA response with two or more consecutive ADA positive sampling time points, separated by greater than (>) 12-week period (84 days), with no ADA negative samples in between.
- b) Indeterminate Response - defined as a treatment-emergent response with only the last collected sample positive in the ADA assay
- c) Transient Response - defined as a treatment-emergent response that is not considered persistent OR indeterminate

Treatment-boosted response is defined as:

A positive response in the ADA assay post first dose that is greater-than or equal to 4-fold over baseline titer levels, when baseline results are positive.

Titer values (Titer value category)

- Low (Titer <1000)
- Moderate ($1,000 \leq \text{Titer} \leq 10,000$)
- High (Titer >10,000)

Samples that are positive in the ADA assay will be further characterized for the presence of anti-dupilumab neutralizing antibodies (NAb).

ADA negative is defined as ADA assay is negative at all times or exhibit a pre-existing immunoreactivity.

ADA positive is defined as either treatment-boosted or treatment-emergent response in the ADA assay.

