- c Patients who permanently discontinue the study medication will be asked and encouraged to return to the clinic for study visits and participate in assessments according to the visit schedule until the end of the study (EOS) with a ±5 day window or up to recovery or stabilization of any adverse event. At the time of permanent treatment discontinuation, patients will perform the early treatment discontinuation (ETD) visit with all the assessments defined for the end-of-treatment (EOT) Visit 28. However, patients who discontinue early from treatment will not be eligible for the 1-year long-term extension study. For patients who permanently discontinue the study, under exceptional circumstances where there is no possibility for a patient and parent(s)/caregiver(s)/legal guardian(s) to come to the site for the scheduled follow-up visit, a phone contact may be made after Sponsor’s approval is given. During that phone contact, at least information about adverse events (AEs), concomitant medication and asthma exacerbation events must be collected, and the schedule for these calls should still reflect the visit schedule. Patients who discontinue early from treatment may be asked to return to the clinic to have additional ADA samples collected for analysis based on the overall assessment of antibody titers and clinical presentation at the time of discontinuation.
- d Eligible patients who complete the Randomized Treatment Period will be offered the opportunity to participate in the 1-year long-term extension study with dupilumab. Patients subsequently enrolled in the 1-year long-term extension study will not participate in the post-treatment period of this trial.
- e The visit windows for all subsequent visits post-randomization on Day 1 will be ±3 days during the treatment period and ±5 days during the post-treatment period.

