- s Assessment of total IgE, antigen-specific IgE, antigen-specific IgG4, and ratio of IgE:IgG4.
- t Systemic drug concentration samples are to be collected prior to dosing and in case of SAE and AESI.
- u Exhaled nitric oxide assessment is conducted prior to spirometry and following a fast of ≥ 1 hour.

- █ [REDACTED]
- w ADA samples are to be collected prior to dosing and in case of SAE and AESI.
 - x For female patients who have commenced menstruating (ie, are of child-bearing potential) at Screening, a urine pregnancy test is mandatory at the Screening Visit 1 with negative result obtained prior to randomization at Visit 2 (Week 0) and at every subsequent visits defined in the flowchart. For female patients who happen to commence menstruating after Screening, a negative urine dipstick pregnancy test will be obtained prior to administration of IMP.
 - y Hematology: hemoglobin, hematocrit, platelet count, total white blood cell (WBC) count with five-part differential count, and total red blood cell count. Serum chemistry: creatinine, blood urea nitrogen, glucose, uric acid, total cholesterol, total protein, albumin, total bilirubin (in case of values above the normal range, differentiation in conjugated and non-conjugated bilirubin), alanine aminotransferase, aspartate aminotransferase, alkaline phosphatase, lactate dehydrogenase, electrolytes (sodium, potassium, chloride), bicarbonate, and creatine phosphokinase. Patients' fasting (considering fasting as no intake of any food or drink except for water for at least 8 hours) or non-fasting status at blood sample collection will be recorded on the Central Laboratory Requisition Form. Clinical laboratory testing only at Screening Visit 1 will include hepatitis screen covering hepatitis B surface antigen (HBs Ag), hepatitis B surface antibody (HBs Ab), hepatitis B core antibody (HBc Ab), hepatitis C virus antibodies (HCV Ab), Human Immunodeficiency Virus (HIV) screen (Anti-HIV-1 and HIV-2 antibodies) and anti-nuclear antibody (ANA).

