10.3.4 Handling of Patients After Permanent Treatment Discontinuation

Patients will be followed-up according to the study procedures as specified in this protocol up to the scheduled date of study completion, or up to recovery or stabilization of any AE to be followed-up as specified in this protocol, whichever comes last. Study Investigators should continue background therapy after treatment discontinuation, as guided by their medical judgment.

For patients in Brazil, see [Appendix N](#).

Patients who permanently discontinue the study medication will be asked and encouraged to return to the clinic for study visits and participate in assessments according to the visit schedule until the EOS with a ± 5 day window or up to recovery or stabilization of any AEs. At the time of permanent treatment discontinuation, patients will perform ETD visit with all the assessments defined for the EOT Visit 28. Patients who permanently discontinue early from treatment will not be eligible for the 1-year long-term extension study.

For patients who permanently discontinue the study, under exceptional circumstances where there is no possibility for a patient and parent(s)/caregiver(s)/legal guardian(s) to come to the site for the scheduled follow-up visit, a phone contact may be made after Sponsor's approval is given. During that phone contact, at least information about AEs, concomitant medication and asthma exacerbation events must be collected, and the schedule for these calls should still reflect the visit schedule.

Patients who discontinue early from treatment may be asked to return to the clinic to have additional ADA samples collected for analysis based on the overall assessment of antibody titers and clinical presentation at the time of discontinuation.

All cases of permanent treatment discontinuation should be entered by the Investigator in the e-CRF when considered as confirmed.

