10.3.5 Procedure and Consequence for Patient Withdrawal From Study

The patients may be withdrawn from the study at any time during the course of study if their parent(s)/caregiver(s)/legal guardian(s) decide to do so, and irrespective of the reason.

Withdrawal of consent for follow-up should be accompanied by documentation of the reason for withdrawal. Withdrawal of consent for treatment should be distinguished from withdrawal of consent for follow-up visits and from withdrawal of consent for non-patient contact follow-up, eg, medical records checks.

For patients who withdraw, the patient and their parent(s)/caregiver(s)/legal guardian(s) should be explicitly asked about the contribution of possible AEs to their decision to withdraw consent, and any AE information elicited should be documented.

Patient(s)/parent(s)/caregiver(s)/legal guardian(s) may withdraw consent verbally or in writing and, if verbal, then the site needs to document in source records that patient withdrew consent verbally.

If possible, the patients who withdraw consent will be assessed using the procedures normally planned for the EOT visit and have EOS assessments completed at the same visit or at the last planned visit.

For patients who fail to return to the site, the Investigator should make the best effort to re-contact the patient (eg, contacting patient's family or private physician, reviewing available registries or health care databases), and to determine his/her health status, including at least his/her vital status. Attempts to contact such patients must be documented in the patient's records (eg, times and dates of attempted telephone contact, receipt for sending a registered letter).

A subject should only be designated as lost to follow-up, if the site is unable to establish contact with the patient/parent(s)/caregiver(s)/legal guardian(s) after 3 documented attempts via 2 different methods (phone, text, e-mail, certified letter, etc).

The statistical analysis plan (SAP) will specify how these patients lost to follow-up for their primary endpoints will be considered. Patients who have withdrawn from the study cannot be rerandomized (treated) in the study. Their inclusion and treatment numbers must not be reused.

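### A treatment-emergent ADA response whose final run of positives spans 84 days or less is labelled transient with no later negative seen, while a single final positive is indeterminate

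*SAP*

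**What the plan says.** SAP 2.1.6 applies three labels to a treatment-emergent ADA response, meaning a positive after the first dose with a negative or missing baseline.

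- Persistent: at least two consecutive positives, "separated by greater than (>) 12-week period (84 days), with no ADA negative samples in between".
- Indeterminate: "defined as a treatment-emergent response with only the last collected sample positive in the ADA assay".
- Transient: "defined as a treatment-emergent response that is not considered persistent OR indeterminate".

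Protocol 11.4.4.2 lists the same classes without defining them.

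Post-baseline ADA samples are planned at Weeks 12, 24, 52 and 64. Children who enter the extension study have no Week 64 visit. Visit windows in the protocol flow chart (1.2, footnote e) are ±"3 days during the treatment period and ±5 days during the post-treatment period". At permanent treatment discontinuation, "patients will perform ETD visit with all the assessments defined for the EOT Visit 28" (Protocol 10.3.4). Where possible, "the patients who withdraw consent will be assessed using the procedures normally planned for the EOT visit" (Protocol 10.3.5). ADA is among the Visit 28 blood samples (Protocol 10.1.13). Footnote w adds that "ADA samples are to be collected prior to dosing and in case of SAE and AESI".

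SAP 2.4.6.1.2 plans a count for each class, peak-titer summaries by class and concentration plots by ADA classification. It also names the three classes among the ADA variables that may be related to drug concentration, exacerbation rate and FEV1.

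**The concern.** Transient is a residual class, so it collects responses for two different reasons. Some were seen to end. Others simply had too little follow-up to pass the 84-day limit. When the final samples are all positive but lie close together, the second reason applies, yet the label suggests the first.

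The ordering is also perverse. A child positive only at the last sample is indeterminate, which is an honest label. An adjoining earlier positive adds evidence that the response is continuing, yet it moves the child to the label that implies a shorter one. Some responses still present at last observation would therefore be reported as transient, and their titers summarized in that class.

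**Working it through.** **Inputs.** Target days for ADA samples are 85, 169, 365 and 449 (SAP 2.5.4, Table 14). The limit is strictly more than 84 days (SAP 2.1.6). Windows are ±3 days on treatment and ±5 days afterwards (flow chart, footnote e).

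**1. The limit.** 12 × 7 = 84 days, as the SAP states.

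**2. Planned gaps.** 169 − 85 = 84; 365 − 169 = 196; 449 − 365 = 84. Two of the three gaps equal the limit, so an on-schedule pair fails the strict inequality.

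**3. Gaps within visit windows.**
- Weeks 12 to 24: 84 ± (3 + 3) = 78 to 90 days. Of 7 × 7 = 49 combinations of visit days, 28 (57.1%) give 84 or less.
- Weeks 52 to 64: 84 ± (3 + 5) = 76 to 92 days. Of 7 × 11 = 77 combinations, 42 (54.5%) give 84 or less.

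These shares treat all days as equally likely and are only illustrative. With the other visits negative, a Week 52 to 64 gap of 84 days gives transient and 85 gives persistent.

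**4. Labels for patterns that end in a positive** (all four samples on target days; the proposed rule is given under the fix).

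| Positive at Weeks | SAP label | Proposed label |
|---|---|---|
| 64 | indeterminate | indeterminate |
| 52, 64 | transient | indeterminate |
| 24, 52, 64 | persistent | persistent |
| 12, 24, 52, 64 | persistent | persistent |
| 12, 64 | transient | transient |
| 24, 64 | transient | transient |
| 12, 24, 64 | transient | transient |
| 12, 52, 64 | transient | transient |

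The seven patterns that end in a negative are 2 persistent and 5 transient under both rules.

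**5. Shorter series.** With samples at Weeks 12, 24 and 52 only, the usual extension entrant, no label changes. With Weeks 12 and 24 only, a single positive at Week 24 is indeterminate, but positives at both are transient.

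**6. Withdrawal samples.** Suppose the first positive is the scheduled sample on day 85 or 169 and the last sample, at withdrawal, is also positive. A withdrawal sample on days 86–169 or 170–253 is at most 84 days later and gives transient. For example, positives on days 85 and 127 are 42 days apart.

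**7. How separation is measured.** The text does not say whether it runs between neighbouring positives or from first to last. Positives on days 85, 169 and 200 span 200 − 85 = 115 days, but the neighbouring gaps are 84 and 31. The first reading gives transient and the second persistent.

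**The case against.** **The general statement would be too broad.** A reader might infer that any child whose last two samples are positive 84 days or less apart is mislabelled. That is not so. Weeks 24, 52 and 64 all positive is persistent, and a child positive at baseline is outside this split.

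**Most of the transient labels that end in a positive can be defended.** Five of the eight patterns in the table are transient under the SAP, which might suggest a widespread fault. Four of those five contain an earlier positive followed by a negative, so a response was seen to disappear. Only Weeks 52 and 64 is a clear case.

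**Withdrawal is the weakest route.** Children who stop treatment are asked to stay on the visit schedule, so their early-discontinuation sample is usually not the last. The route needs study withdrawal, where the visit happens only if possible. In addition, the SAP speaks of sampling time points. If these meant Table 14 windows (up to day 126, then 127–266), a withdrawal sample on days 86–126 or 170–253 would share a window with the earlier positive. That covers 41 + 84 = 125 of the 168 days, and some of these children might then count as having one final positive. Table 14 is stated to be for by-visit summaries, so this reading is doubtful, but it is not excluded. It leaves the Weeks 12 and 24 and Weeks 52 and 64 cases untouched, since each of those samples has its own window.

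**Other outputs soften the effect.** SAP 2.1.6 lets early discontinuers and children not entering the extension be recalled for further ADA samples, and SAP 2.4.6.1.2 reports treatment-emergent positivity at each visit. Recall is discretionary, and per-visit positivity does not correct the class counts.

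These points narrow the finding. None of them changes how the rule labels a final run of 84 days or less.

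**Conclusion.** The rule as written gives the wrong label to a treatment-emergent response whose final unbroken run has two or more positives spanning 84 days or less, with no earlier persistent run. The clear cases are those where that run contains the only positives:

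- Weeks 52 and 64 positive, earlier samples negative, in a child who does not enter the extension.
- Weeks 12 and 24 positive with no later sample.
- A first positive confirmed at a last withdrawal sample up to 84 days later, subject to the time-point reading discussed above.

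The outputs touched are the class counts, the class-specific peak titers, the concentration plots and the optional exploratory associations with concentration, exacerbation rate and FEV1. Overall ADA incidence, titer categories, neutralizing status and the hierarchical tests do not use the split.

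The number of children is unknown and probably small. A reader might try to size the withdrawal route from the 20% discontinuation in Protocol 11.1: 268 × 0.20 × 168/364 = 24.7 dupilumab children leaving in the relevant span. The documents do not support that use. The 20% is a sample-size assumption about exposure, not a forecast of study withdrawal, and no ADA rate is given to apply to it. Extension uptake, which governs how many children reach Week 64, is not given either. This is a minor point, worth correcting because it costs little.

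**What to change.** Keep the limit of more than 84 days. State that separation is counted from the first to the last actual sampling date of an unbroken run of positive samples, and replace the three definitions in SAP 2.1.6 with:

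- (a) Persistent: a treatment-emergent response with an unbroken run of two or more positive samples spanning more than 84 days.
- (b) Indeterminate: a treatment-emergent response that is not persistent and whose only positives are one unbroken run ending at the last collected sample.
- (c) Transient: any other treatment-emergent response.

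Using actual dates also settles the time-point and neighbouring-gap questions. Positive-negative-positive patterns stay transient as now.

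The cost is a few lines of SAP text and of the ADA derivation, with no new data. A few children move from transient to indeterminate. With all four samples on schedule, only the Weeks 52 and 64 pattern moves. Visit timing can still decide between persistent and indeterminate for that pair, because its planned gap sits on the limit.
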